11.5 Calculation or derivation of health economic variable

See Section [6.5](#).

11.6 Calculation of CAP-Symptom 18 variables

See Section [6.6](#)

12. STATISTICAL METHODS AND SAMPLE SIZE DETERMINATION BY ASTRAZENECA

[figure not shown]
12.1 Description of analysis sets

12.1.1 Efficacy analysis set

The following figure shows the relationship among efficacy analysis sets graphically.

Figure 2 Efficacy analysis sets

The detailed definition of each efficacy analysis set is described as below.

12.1.1.1 Intent-to-Treat (ITT) Population

The ITT Population will consist of all randomised patients. A patient is considered randomised when the Pharmacist or Pharmacist’s designee receives the IVRS/IWRS-generated patient number.

12.1.1.2 Modified Intent-to-Treat (MITT) Population

The MITT Population will consist of all randomised patients who receive any amount of study drug.

12.1.1.3 Microbiological Modified Intent-to-Treat (mMITT) Population

The mMITT Population will be a subset of the MITT Population and will include patients for whom at least one “typical” bacterial pathogen has been isolated from an appropriate microbiological specimen (eg, blood, sputum, or pleural fluid) and urinary antigen testing and who meet the minimal disease criteria for CABP. Patients with *M. pneumoniae* or *C. pneumoniae* or *L. pneumophila* as the sole causative pathogen of infection will be excluded from the mMITT Population.

12.1.1.4 Clinically Evaluable (CE) Population

The CE Population will be a subset of the MITT Population and will include patients who meet the minimal disease criteria for CABP and all evaluability criteria, including patients

who received at least the pre-specified minimal amount of the intended-dose and duration of study drug therapy, for whom sufficient information regarding the infection is available to determine the patient's outcome, and for whom there are no confounding factors that interfere with the assessment of that outcome; patients with an atypical pathogen as a sole causative pathogen of the infection will be excluded from the CE Population.

In addition to meeting the above criteria, patients must meet the following specific conditions:

- At least 48 hours of study drug therapy received in order to be considered an evaluable clinical failure, unless deemed a clinical failure based on a treatment-limiting AE
- At least 72 hours of study drug therapy received in order to be considered an evaluable clinical cure
- At least 80% of the intended doses of study drug therapy received. Compliance is determined as the total number of received doses divided by the total number of intended doses based on the first and last date and time of study drug administration
- Clinical response assessment at TOC (8 - 15 days after EOT), or a clinical failure at EOT or at any time up to 15 days after EOT is allowed. For patients who died a 28 day window up to and including 28 days after EOT is allowed
- A patient with an indeterminate response at TOC is not included in the CE population unless the reason for the indeterminate response is "Death where CABP is non causative"
- Did not receive more than one dose of an alternative (non-study) systemic antimicrobial that was potentially effective for the treatment of CABP, for a reason other than treatment failure.

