5.8.1 Guidance to Investigators on When to End Study Drug Therapy

Patients who are improving clinically will receive at least 5 days but not more than 7 days of study drug therapy. Study drug therapy should continue until all signs and symptoms of the baseline infection have resolved or improved to such an extent that no further antimicrobial therapy is necessary. Prior to ending study drug therapy, the patients must:

- Be afebrile (temperature $\leq 38^{\circ}\text{C}$ oral or $\leq 38.5^{\circ}\text{C}$ rectally or tympanically) for at least 24 continuous hours, with temperature recorded twice daily
- Have had resolution of all signs and symptoms of CABP, or substantial improvement in signs and symptoms of CABP, such that the Investigator considers antibiotic therapy to be no longer required. Substantial improvement includes a return to pre-CABP baseline levels for patients with decreased pulmonary function (eg, patients with chronic obstructive pulmonary disease).

An insufficient therapeutic effect may be determined prior to the planned EOT visit. This determination will require an assessment of clinical status including the synthesis of symptoms and signs data (both local and systemic) and available laboratory data. Patients who are deemed to have an insufficient therapeutic effect should be considered treatment failures and discontinued from study drug therapy. For the purposes of this study, the following categories and guidelines are provided:

- **Clinical Worsening:** Patients who show systemic or local signs of clinical worsening may be prematurely discontinued from study drug therapy at any time. If the Investigator deems the benefit-to-risk ratio of continuing study drug therapy acceptable, administration of study drug for at least 48 hours is encouraged prior to discontinuation
- **Lack of Clinical Progress:** For patients who are stable, yet do not show signs of improvement, the Investigator is encouraged to continue study drug therapy for a minimum of 72 hours before such patients are considered clinical failures and prematurely discontinued from study drug

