6.3.2 Clinical Response Definitions

6.3.2.1 Clinical Response at the EOT and TOC Assessments

Clinical outcome assessments (see [Table 5](#)) will be made by the Principal Investigator at the EOT and TOC visits. Clinical response will be classified as cure, failure, or indeterminate based on clinical outcome. A favourable clinical response is “clinical cure”. A clinical failure occurring at an earlier time point will be carried forward to the TOC visit.

Table 5 Clinical Response Assessments at the EOT and TOC Visits

Outcome	Definition
Clinical Cure	Total resolution of all signs and symptoms of pneumonia (ie, CABP), or improvement ^a to such an extent that further antimicrobial therapy is not necessary
Clinical Failure ^b	Any of the following: * Persistence, incomplete clinical resolution, or worsening in signs and symptoms of CABP that requires alternative antimicrobial therapy * Treatment-limiting AE leading to discontinuation of the study treatment regimen, when patient required alternative antimicrobial therapy to treat the pneumonia * Death wherein pneumonia (ie, CABP) is considered causative
Indeterminate	Study data are not available for evaluation of efficacy, for any reason including treatment change prior to completing at least 48 hours of the study treatment regimen; death wherein pneumonia is clearly non-contributory, lost to follow-up, or extenuating circumstances preclude classification as a cure or failure

^a Clinical improvement includes the absence of fever (temperature $\leq 38^{\circ}\text{C}$ oral or $\leq 38.5^{\circ}\text{C}$ rectally or tympanically) for at least 24 continuous hours, with temperature recorded twice daily, in addition to a substantial improvement in signs and symptoms of CABP. Substantial improvement includes a return to pre-CABP baseline levels for patients with decreased pulmonary function (eg, patients with chronic obstructive pulmonary disease).

^b Clinical failures at EOT are carried forward to TOC.

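### The CE definition drops pneumonia deaths before 48 hours of study drug, leaves the status of non-pneumonia deaths unsettled, and Table 5 gives an early AE-driven switch two outcomes

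*Protocol*

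**What the plan says.** Table 5 (Protocol section 6.3.2.1) assigns the clinical outcome. Three of its entries matter here:

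- The failure row includes "Death wherein pneumonia (ie, CABP) is considered causative", with no time limit.
- The failure row also includes a treatment-limiting AE that stops study treatment when the patient needs another antimicrobial for the pneumonia, again with no time limit.
- The indeterminate row includes "treatment change prior to completing at least 48 hours of the study treatment regimen", with no exception for AEs, and "death wherein pneumonia is clearly non-contributory".

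Section 12.1.1.4 then decides who enters CE. Its list is cumulative: "In addition to meeting the above criteria, patients must meet the following specific conditions". The first condition is "At least 48 hours of study drug therapy received in order to be considered an evaluable clinical failure", with one exception: "unless deemed a clinical failure based on a treatment-limiting AE". A later condition reads "A patient with an indeterminate response at TOC is not included in the CE population unless the reason for the indeterminate response is" a death that CABP did not cause.

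Section 12.2.2.2, under the EOT cure rate, states that CE by definition holds no indeterminates, and Table 10 lists that category for MITT only. Sections 2.1 and 12.2.2.1 make CE the sole population for the non-inferiority conclusion. The MITT cure rate at TOC is secondary.

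**The concern.** A death from the disease under study is the clearest treatment failure in the trial, yet before 48 hours it is removed from the primary analysis. An AE failure at the same time point is kept, and a death from another cause has its own route past the indeterminate exclusion. The protocol gives no reason for treating these cases differently.

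In addition, the protocol's own text can place one patient either inside or outside CE. This applies to the early AE-driven switch (Table 5) and to the non-pneumonia death (12.1.1.4 against 12.2.2.2). Investigators assign the Table 5 outcome, so two sites could classify identical patients differently.

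At stake is who counts in the population that decides non-inferiority. The exclusion follows randomisation and depends on outcome, so it could shift the estimated difference if early failures were unequal between arms.

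**Working it through.** **Reading the passages together**

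1. *CABP death before 48 hours of drug.* Table 5: failure. Section 12.1.1.4, first condition: not evaluable, because death is not among the exceptions. The 28-day window for deaths in the same list sets how late a death may count; since all conditions must hold, it does not waive the first. Result: out of CE.
2. *Death not due to CABP.* Table 5: indeterminate. Section 12.1.1.4 lifts the indeterminate exclusion; section 12.2.2.2 says no indeterminates are in CE. The protocol gives no formula for the CE cure rate. The ME formula, for a population that must also satisfy CE, has only cures and failures in its denominator. Whether such a death is in CE, and whether it counts as a non-cure, is unsettled.
3. *Treatment-limiting AE with a switch before 48 hours.* Failure row: in CE through the AE exception, if the other conditions are met. Indeterminate row: out of CE.
4. *Clinical worsening with a switch before 48 hours, no AE.* If called failure, the 48-hour condition excludes it; if called indeterminate, the indeterminate condition excludes it. In MITT both labels are in the denominator and not the numerator. No rate changes.

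**Arithmetic**

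Inputs: cure 85% in both arms, margin 10 points, power 90%, evaluability 77.5% (section 12.3); two-sided 95% CI (section 12.2); lower limit of -10% or higher (section 12.2.2.1).

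5. *The plan's own figure.* n per arm = (1.960 + 1.282)² × (2 × 0.85 × 0.15) / 0.10² = 267.94, so 268 evaluable. 268 / 0.775 = 345.8, so 346 per arm and 692 in total. This reproduces the protocol; the sample size is not in question.
6. *One excluded failure.* 228/268 = 85.07%; counting one more failure, 228/269 = 84.76%. Change: 0.32 points in that arm.
7. *Balanced losses.* Take 222/268 against 228/268, a difference of -2.24 points. Adding three failures to each arm gives 222/271 - 228/271 = -2.21 points, practically unchanged. If a common early-failure rate e is counted, the cure rate is p = 0.85(1 - e), the arm size is M = 268/(1 - e), and power is Φ(0.10/√(2p(1 - p)/M) - 1.96). For assumed e of 0.5%, 1%, 2% and 3%, power is 89.5%, 89.0%, 88.0% and 87.1%.
8. *Unbalanced losses, assumed all on ceftaroline.* Unstratified Miettinen-Nurminen lower limits, ceftriaxone fixed at 228/268:

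| Ceftaroline cures of 268 | Lower limit | Excluded failures that, if counted, take it below -10% |
|---|---|---|
| 219 | -9.72% | 1 |
| 220 | -9.32% | 3 |
| 222 | -8.52% | 5 |
| 228 | -6.10% | 13 |

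9. *One-sided error under the same one-arm assumption.* Let the true rates with early failures counted be 85% and 75%, exactly at the margin. Dropping a ceftaroline-only excess e makes the CE rate 0.75/(1 - e). By normal approximation with 268 per arm, e of 0.5%, 1%, 2% and 3% gives an error of about 3.2%, 4.1%, 6.6% and 10.2% instead of 2.5%.

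The protocol gives no rate of death or failure before 48 hours. Steps 7 to 9 are therefore ranges over assumptions, not estimates.

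**The case against.** The strongest case for the plan is that outcome and evaluability are different things. A CABP death at hour 24 can consistently be a failure that is not evaluable, and a minimum-exposure rule in an evaluable population is ordinary practice. That stands: the rule as such is no error. It does not explain why an early AE failure is excepted and an early CABP death is not.

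Other points also stand:

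- Table 5's AE failure row agrees with 12.1.1.4. The conflict is an overlap with the indeterminate row, not a flat contradiction. Read alone, 12.1.1.4 keeps early AE failures.
- Section 4.2 excludes PORT class V, patients requiring ICU admission and immediately life-threatening disease, so CABP deaths before 48 hours are likely rare.
- The MITT analysis counts all these patients as non-cures and is reported with a CI. It has no stated role in the non-inferiority decision.
- Evaluability is decided before the codes are broken (section 5.4.2). This guards against selective exclusion, though not against unequal early failure.

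Three stronger readings may tempt a reader, and the document supports none of them:

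- *That the rule biases the test towards non-inferiority.* This needs an excess of early failures on ceftaroline. An excess on ceftriaxone would work the other way, and balanced losses favour neither arm.
- *That CE expressly admits a non-pneumonia death at hour 24.* The opening paragraph of 12.1.1.4 still requires a minimal dose and duration; only the indeterminate exclusion is lifted.
- *That section 5.8.1 adds a further conflict affecting the result.* It says "Patients who are deemed to have an insufficient therapeutic effect should be considered treatment failures and discontinued from study drug therapy", while Table 5 may label an early switch indeterminate. By step 4, neither label changes the CE or MITT cure rate.

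**Conclusion.** The point holds as a defect of definition in the primary population. The loss of early CABP deaths follows directly from Table 5 and 12.1.1.4. The status of non-pneumonia deaths is contradicted between 12.1.1.4 and 12.2.2.2, and an early AE-driven switch can be placed in or out of CE.

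The effect is about 0.3 points of one arm's CE cure rate per excluded failure. It can decide the conclusion only when the lower limit is already close to -10% (one to five patients in one arm for limits between -9.7% and -8.5%) or when losses are clearly unbalanced. Those figures assume 268 per arm, ceftriaxone cure near 85%, no stratification and every loss on ceftaroline. The direction and size of any actual bias cannot be determined from the protocol. The point is worth correcting before evaluability is decided, but it does not undermine the design. A SAP may already settle it; the protocol text would still need to agree.

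**What to change.** Three changes to the analysis definitions, made before evaluability decisions and unblinding:

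1. In the first CE condition of 12.1.1.4, extend the exception so that it also covers a clinical failure due to a death attributed to CABP.
2. In Table 5's indeterminate row, take out of the under-48-hour category any treatment change that satisfies the treatment-limiting-AE entry of the failure row.
3. Reconcile 12.2.2.2 (with Table 10) and 12.1.1.4: state whether deaths not caused by CABP are in CE and, if so, how they count in the CE cure rate. Align the ME wording.

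Section 5.8.1 needs no change for this purpose. Patient care, data collection and the planned 692 patients are unaffected. The cost is a slightly lower CE cure rate, the inclusion of a few patients with short exposure and, if early failures are balanced at 0.5% to 3%, power of about 89.5% to 87.1% instead of 90%.

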Ceftriaxone for Injection is supplied as 1 g/vial (2 vials for a 2 grams dose) and a 2 grams dose will be infused over 30 (± 10) minutes q24h (± 2 h). IV saline placebo will also be infused to maintain blinding. It is not necessary to make dose adjustments of ceftriaxone for patients with mild ($50 \text{ mL/min} < \text{CLCR} \leq 80 \text{ mL/min}$) or moderate ($30 \text{ mL/min} < \text{CLCR} \leq 50 \text{ mL/min}$) renal insufficiency.

Study Drug Dosing Overview in Patients with Normal Renal Function

Treatment Group	First Daily Dose		Second Daily Dose	
	Infusion 1	Infusion 2	Infusion 1	Infusion 2
	30 (± 10) min	30 (± 10) min	30 (± 10) min	30 (± 10) min
Ceftaroline fosamil	Ceftaroline 300 mg	Ceftaroline 300 mg	Ceftaroline 300 mg	Ceftaroline 300 mg
Ceftriaxone	Ceftriaxone 2 g	Placebo	Placebo	Placebo

Duration of treatment

Baseline assessments for study eligibility will occur within 24 hours prior to administration of the first dose of study drug therapy. The duration of treatment with study drug is 5 to 7 days. An EOT visit will occur on the last day the study treatment regimen is administered. The

TOC visit will occur 8 to 15 days after the last dose of study drug is administered, and an LFU visit will occur 21 to 35 days after the last dose of study drug is administered (see [Table 1](#)). Patient participation will require between 26 and 42 days.

Discontinuation of investigational product, Guidance to investigators on when to end study drug therapy and information regarding the complete withdrawal from the study (withdrawal of informed consent) are described in Sections [5.8](#), [5.8.1](#), and [5.9](#) respectively).

Outcome variable(s):

Primary Endpoint

The primary efficacy endpoint will be the per-patient clinical cure rate at the TOC visit in the CE population.

Secondary Endpoints:

Efficacy:

- Per-patient clinical cure rate at the TOC visit in the MITT, mMITT and ME Populations
- Per-patient clinical cure rate at the EOT visit in the CE and MITT Populations
- Per-patient microbiological favourable outcome rate at the TOC visit in the mMITT and ME Populations
- Per-patient overall success rate at the TOC visit in the CE and MITT populations
- Per-pathogen clinical cure rate and microbiological favourable outcome at the TOC visit in the ME and mMITT populations
- Per-patient clinical relapse rate at the LFU visit in the CE and MITT populations who were clinically cured at the TOC visit

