Vital signs ^m	X	X	X	X	X	X	X	X	
Pulse oximetry ⁿ	X	X	X	X	X	X	X	X ⁿ	
12-lead ECG ^o	X			X			X	X	
CXR or CT scan ^p	X							X	X
Laboratory tests ^q	X			X			X ^r	X	
Additional laboratory tests (blood) ^s	X ^s						X ^s	X ^s	X ^s
CL _{CR} estimated ^t	X			X			X		
Pregnancy test ^u	X						X		
L. pneumophila & pneumococcal UAT ^v	X								
Sputum specimen ^w	X	X ^w	X ^w	X ^w	X ^w	X ^w	X ^w	X ^w	X ^w
Pleural fluid specimen ^x	X ^x	X ^x	X ^x	X ^x	X ^x	X ^x	X ^x	X ^x	X ^x
Blood for culture ^y	X	X ^y	X ^y	X ^y	X ^y	X ^y	X ^y	X ^y	X ^y
Record adverse events ^z	X	X	X	X	X	X	X	X	
Record SAEs	X	X	X	X	X	X	X	X	X
Administer study drug		X ^a	X	X	X	X	X ^{aa}		
Resource Use									X
PK sample ^{bb}				X					

^a Baseline: completed within 24-hours prior to infusion of the first dose (Day 1) of study drug

- b EOT must be performed on the last day the study drug therapy is administered (if the last dose occurs at night, except ECG recording, these can be performed in the a.m. of the following day). If discontinuing early or withdrawing, the patient should have all EOT assessments performed on the day of discontinuation or withdrawal
- c TOC: 8 to 15 days after administration of the last dose of study drug
- d LFU performed 21 to 35 days after administration of the last dose of study drug
- e Written informed consent must be obtained prior to any study procedures or assessments
- f CAP-Symptom 18 questionnaire should be completed prior to any other study related procedures (see [Appendix I](#))
- g Verify patient meets all eligibility criteria prior to randomisation
- h Record prior medications taken within 4 weeks prior to baseline
- j Complete physical exam performed at baseline, including height and weight measurements; brief physical exam performed on Day 3 (± 1 day), EOT and LFU. For definitions of each type of physical exam, see Section 6.4.6 and [Appendix H](#)
- k CABP signs and symptoms include, but may not be limited to: cough, pleuritic chest pain, dyspnoea and sputum production and character.
- All signs and symptoms from the episode prior to this current CABP diagnosis must also be recorded at baseline.
 - Categorize the symptom intensity by using the AE variables (see Section 6.4.3) of Absent, Mild, Moderate or Severe.
 - For the purposes of this study, also record patient's ability to maintain oral intake and mental status. Categorize their mental status as normal or altered (reference definition of mental status in [Appendix D](#)).

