1.5 End of Therapy (EOT)

Administration of study drug may occur on the same calendar day as the EOT visit, and if so will be completed before the EOT assessments begin. If the last dose of the study drug or treatment regimen occurs at night, the EOT assessments (with the exception of the ECG recording) can be performed in the morning of the following day.

1. Unless deemed a treatment failure, administer study drug therapy: Infusion 1 over 30 (\pm 10) minutes immediately followed by Infusion 2 over 30 (\pm 10) minutes, q12h (\pm 2 hours). If a treatment failure, complete EOT visit assessments
2. Administer CAP-Symptom 18 questionnaire prior to any other study related procedures (see [Appendix I](#)). This questionnaire should be read to the patient and the patient is to provide a response without any assistance or interpretation
3. Record any new concomitant medications
4. Perform a brief physical examination including:
 - General appearance, including skin
 - Cardiovascular system
 - Lungs
 - Abdomen
5. Evaluate and record their CABP signs and symptoms, which include, but may not be limited to, cough, pleuritic chest pain, dyspnoea and sputum production and character. Categorize the symptom intensity by using the AE variable of Absent, Mild, Moderate or Severe (see Section 6.4.3). For the purposes of this study, also record patient's ability to maintain oral intake and mental status. Categorize their

mental status as normal or altered (reference definition of mental status in [Appendix D](#))

6. Record resting vital signs including heart rate, blood pressure (measure after patient has been in a supine position for 5 minutes), respiratory rate, oxygen saturation, and temperature (oral, rectal or tympanic). Measure the patient's temperature (oral, rectal, or tympanic) in the morning and afternoon, record the highest daily temperature (oral, rectal, or tympanic)
7. Obtain one 12-lead ECG recording within 60 minutes of the end of Infusion 2
8. Laboratory tests: Do not obtain EOT laboratory tests if previous laboratory tests were within prior 24 hours. If not, obtain blood and urine samples as required by the Schedule of Assessments, see Table 1 and reference the Laboratory Manual for specific information on the collection, processing, handling, storage and shipping of samples, see Section 7.1 for blood volumes and [Appendix G](#) for identification of laboratory tests

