1.6 Test of Cure (TOC)

Perform TOC assessments 8 to 15 days after the last dose of the study treatment regimen is administered.

1. Administer CAP-Symptom 18 questionnaire prior to any other study related procedures (see [Appendix I](#)). This questionnaire should be read to the patient and the patient is to provide a response without any assistance or interpretation
2. Record any new concomitant medications
3. Perform a brief physical examination including:
 - General appearance, including skin
 - Cardiovascular system
 - Lungs
 - Abdomen
4. Evaluate and record their CABP signs and symptoms, which include, but may not be limited to, cough, pleuritic chest pain, dyspnoea and sputum production and character. Categorize the symptom intensity by using the AE variable of Absent, Mild, Moderate or Severe (see Section 6.4.3). For the purposes of this study, also record patient's ability to maintain oral intake and mental status. Categorize their mental status as normal or altered (reference definition of mental status in [Appendix D](#))
5. Record resting vital signs including heart rate, blood pressure (measure after patient has been in a supine position for 5 minutes), respiratory rate, oxygen saturation (if medically indicated), and temperature (oral, rectal or tympanic). Measure the patient's temperature (oral, rectal, or tympanic) in the morning and afternoon, record the highest daily temperature (oral, rectal, or tympanic)
6. Obtain one 12-lead ECG recording
7. Obtain CXR posteroanterior or chest CT scan, unless the subject was deemed a failure at the EOT visit. If the patient's condition does not allow for a standard posteroanterior, a portable anteroposterior CXR is acceptable
8. Laboratory tests: obtain blood and urine samples as required by the Schedule of Assessments, see Table 1. Reference the Laboratory Manual for specific information on the collection, processing, handling, storage and shipping of samples, Section 7.1 for blood volumes, and [Appendix G](#) for identification of laboratory tests
9. Additional laboratory tests: obtain additional blood and urine samples as required by the Schedule of Assessments, see Table 1, along with any other medically indicated as determined by the Investigator. Reference the Laboratory Manual for specific information on the collection, processing, handling, storage and shipping of

samples, Section 7.1 for blood volumes, and [Appendix G](#) for identification of laboratory tests

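### The clinically evaluable (CE) population counts the test-of-cure window from EOT, the visit schedule counts it from the last dose, and when EOT slips to the next morning an on-schedule day-8 cure falls outside CE

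*Protocol*

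**What the plan says.** For site scheduling, the protocol uses one anchor throughout, the last dose:

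- Synopsis, duration of treatment: "TOC visit will occur 8 to 15 days after the last dose of study drug is administered".
- Section 3.1, Table 1, footnote c: "TOC: 8 to 15 days after administration of the last dose of study drug". The text of Section 3.1 uses the same anchor.
- Appendix H, Section 1.6: "Perform TOC assessments 8 to 15 days after the last dose of the study treatment regimen is administered".

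For membership of the primary analysis population, Section 12.1.1.4 uses a different anchor: "Clinical response assessment at TOC (8 - 15 days after EOT". The same bullet then treats failures more generously: "or a clinical failure at EOT or at any time up to 15 days after EOT is allowed". For patients who die it allows 28 days, also counted from EOT.

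On the timing of EOT itself, Table 1 footnote b sets the rule: "EOT must be performed on the last day the study drug therapy is administered". The same footnote and Appendix H, Section 1.5 add an exception for a last dose given at night: "the EOT assessments (with the exception of the ECG recording) can be performed in the morning of the following day".

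**The concern.** A visit window and the analysis window that judges it should share a reference date. Here they can differ by one day, and the patients affected are those for whom the site used a permitted option.

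The bullet also works unevenly by outcome. A cure needs a TOC assessment on or after day 8 from EOT. A failure has no lower limit. For two patients with the same dates, both seen on the first permitted day, the one who failed stays in CE and the one who was cured leaves it. Membership of the primary population then depends on the outcome among patients who followed the protocol. The Microbiologically Evaluable population inherits this, because Section 12.1.1.5 requires CE membership.

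At stake are some precision, a slightly lower CE cure rate, and the consistency of evaluability decisions. Section 5.4.2 requires those decisions patient by patient before the code is broken. Two people applying the text as it stands could classify the same patient differently.

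**Working it through.** **1. Dates.** Let day 0 be the date of the last dose.

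| Case | Permitted TOC visit (days after last dose) | CE window for a cure (days after last dose) |
|---|---|---|
| EOT on day 0 | 8 to 15 | 8 to 15 |
| EOT on day 1 (night-time last dose) | 8 to 15 | 8+1 to 15+1, so 9 to 16 |

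In the second row, day 8 is on schedule but outside CE for a cure and inside CE for a failure. Day 16 is off schedule but inside CE. One of the eight permitted visit days is lost.

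**2. The plan's own sample size.** Inputs from Section 12.3: cure rate 85% in both arms, margin 10%, power 90%, evaluability 77.5%. From Section 12.2: two-sided 95% confidence interval.

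- n per arm = (1.960 + 1.282)² × (2 × 0.85 × 0.15) / 0.10² ≈ 267.9, rounded up to 268 evaluable.
- 268 / 0.775 = 345.8, rounded up to 346 per arm, so 692 in total. This matches the protocol.
- Power at 268 per arm: Φ(0.10 / √(0.255/268) − 1.96) = 90.0%.

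**3. Size of the loss.** The protocol does not say how often EOT is done the next morning or how TOC visits spread over the window. Both are therefore assumptions:

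- f = share of patients with next-morning EOT
- g = share of those seen on day 8 (1/8 = 12.5% if visits spread evenly over the eight days)

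Only cures are removed:

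- cures lost per arm = 268 × 0.85 × f × g = 227.8 × f × g
- n′ = 268 − cures lost
- p′ = (227.8 − cures lost) / n′
- power = Φ(0.10 / √(2p′(1−p′)/n′) − 1.96)

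| f | g | Lost, both arms | n′ per arm | CE cure rate | Power |
|---|---|---|---|---|---|
| 10% | 5% | 2.3 | 266.9 | 84.9% | 89.8% |
| 25% | 12.5% | 14.2 | 260.9 | 84.6% | 88.6% |
| 50% | 12.5% | 28.5 | 253.8 | 84.2% | 87.0% |

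The cure rate has to move along with n. Reducing n while holding cure at 85% would describe a rule that drops patients regardless of outcome, which this one does not, and it would understate the loss of power.

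**The case against.** The strongest reply is that by the protocol's own rule the two anchors are the same day. EOT is to be done on the last dosing day, and Section 5.8 repeats this for early discontinuation. The next-morning option is an exception. It can fairly be read as moving the assessments while the end-of-therapy date stays where it was, and on that reading the conflict disappears. This stands as a possible reading, but the text does not settle it. EOT is introduced as a visit, and the same bullet speaks of a failure at EOT, which is the visit assessment of Section 6.3.2.1. If the last dose was meant, the bullet should say so.

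The effect on inference is also limited. Infusion schedules match in the two arms and assessors are blinded. Evaluability is already set at 77.5%. Clinical cure at TOC is also analysed in the MITT population, whose definition has no visit-window condition. All of this stands.

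A reader might infer three stronger things that the document does not support:

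- **That every patient seen on the first permitted day is lost.** Several conditions must hold together: EOT read as the visit date, a night-time last dose, assessments deferred to the morning, TOC on exactly day 8, and a cure.
- **That next-morning EOT is common because infusions are given every 12 hours.** No section gives its frequency or requires the final dose to be an evening one.
- **That the comparison is biased between arms.** Nothing suggests that the arms would differ in EOT timing or in the day of the TOC visit.

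Finally, no other section gives a competing anchor for the 15-day failure limit or the 28-day death limit. Changing those is for consistency and does not resolve a contradiction.

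**Conclusion.** The mismatch is in the text and should be corrected. Its consequence is confined to patients whose EOT was done the morning after a night-time last dose, and it arises only if EOT is taken as the visit date. Within that group, the rule removes on-schedule day-8 cures and keeps failures seen on the same day.

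The effect is modest and its size rests wholly on assumed frequencies. It ranges from negligible to a loss of about 3 percentage points of power and about 0.8 points of CE cure rate across the cases shown. It concerns precision, the level of the CE cure rate and reproducible evaluability decisions. It does not show a treatment-related bias, and the sample size is correct as stated.

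**What to change.** In Section 12.1.1.4, count the TOC assessment window from the last dose of study drug, so that the CE window equals the visit window in the synopsis, Section 3.1, Table 1 and Appendix H. Use the same anchor for the 15-day failure limit and the 28-day death limit in that bullet, so that one reference date serves the whole criterion.

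With this change no on-schedule patient is lost through the choice of anchor. At 268 evaluable per arm the power stays at 90.0%, and 692 is unchanged. No visit or treatment changes.

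The cost is a small wording amendment before unblinding. If it is judged substantial, Section 8.5 requires ethics committee approval and, where applicable, regulatory approval. The analysis plan, which Section 12.2 requires to be final before unblinding, should derive the date in the same way.
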